146 The adolescents used the system for a median 75.8% of the time, and adults used the
147 system for a median 88.0% of the time. From baseline run-in to the end of study phase the
148 adolescent HbA1c decreased from 7.7% to 7.1% ($P < 0.001$) and adult HbA1c levels
149 decreased from 7.3% to 6.8% ($P < 0.001$). The proportion of overall in-target (71–180
150 mg/dL) sensor glucose (SG) values increased from 60.4% to 67.2% ($P < 0.001$) in
151 adolescents and from 68.8% to 73.8% ($P < 0.001$) in adults. Figure 1-4 provides a graph of
152 the sensor values for both adolescent and adult subjects comparing their baseline data to
153 their data using the 670G. There were no severe hypoglycemic or diabetic ketoacidosis
154 events in either cohort.

155

156 **Figure 1-4:** Graph of the median and interquartile range sensor values over a 24 hour day
157 comparing the values obtain at baseline with regular care (in grey), to the data over 3
158 months of using the Medtronic 670G pump for the adult and adolescent patients. The gray
159 band and dotted line represent data from the run-in phase; the pink band and solid line
160 represent data from the study phase. ⁷

161

162 1.2.3 Use Of A Standard Breakfast To Assess Insulin Pharmacodynamics Data 163 In An Outpatient Setting.

164 In a study to assess the effect of hyaluronidase administration on insulin
165 pharmacodynamics, 14 subjects were instructed to eat the same breakfast meal each day,
166 give an insulin bolus based on their usual insulin-to-carbohydrate ratio and correction
167 factor, and they were instructed not to eat for at least 3 hours following breakfast. Subjects
168 were required to document their food intake each morning at breakfast and the
169 carbohydrate content was verified on the pump download bolus history. Postprandial
170 glucodynamic parameters including peak glucose concentration (C_{max}), time to C_{max} (t_{max}),

171 and estimated average glucose excursions were assessed using sensor glucose values at
 172 a time interval of 0 to 180 minutes after breakfast bolus. If a bolus was given between 120-
 173 180 minutes following the breakfast bolus, CGM values were only used up to the time of the
 174 bolus. The glucose at the time of the breakfast bolus (Time 0) was set to 0 mg/dL for each
 175 meal, and the remaining CGM values were adjusted proportionally to allow analysis of
 176 postprandial glucodynamic parameters. We utilized a mixed-effects model accounting for

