461 more than 10 mm of erythema or induration. They will be given a ruler for making
462 these measurements. If there is more than 3 mm of induration or redness they will
463 be asked to take a picture and enter these measurements into a text to the study

464 coordinator or submit the information directly into RedCap.

465

466 The goal will be to have sensor wear at least 80% of the time and in automode at
467 least 70% of the time. The pump will be uploaded to a research Carelink account
468 each week. While in the blinded phase of the study the clinical staff will refrain from
469 making changes to 670G pump settings unless requested by the subject or for
470 safety reasons such as an episode of severe hypoglycemia (unconsciousness or
471 seizure), >10% time <70 mg/dl, or >20% of the time over 250 mg/dl.

472

473 **Part 1: Randomized, cross-over, blinded study to assess any adaptations of**
474 **the 670G pump to Fiasp® and to assess meal pharmacodynamics of Fiasp®**
475 **compared to aspart with a typical breakfast in the home environment**

476

477 Participants will have a 2 week run-in on their usual home insulin (aspart of Fiasp®).
478 During the run-in, their pump will be downloaded weekly, reviewed by the clinical
479 staff and adjustments will be made to their settings as needed to optimize their
480 glycemic control. Participants will then be randomly assigned to 2 sequences of
481 testing starting with either aspart or Fiasp®. They will use each insulin for two
482 weeks. The participants and the investigators will be blinded to the insulin. During
483 the second week of using a blinded insulin they will have the meal
484 pharmacodynamics testing. They will then cross-over to the other insulin and
485 during the second week they will repeat meal pharmacodynamics testing. At the
486 end of each week they will upload their 670G pump to a Carelink clinical (research)
487 account and it will be reviewed by the research staff for safety purposes.

488

489 Procedure for meal testing. For each week of meal testing they will be asked to
490 have 3 days with a consistent breakfast that is the same for all 6 days they are
491 doing a meal test (3 days on each insulin). The breakfast studies should ideally
492 occur on standard work days (not holidays or weekends). On these three days they
493 will be asked to have a dinner with at least 30 grams of fat and no additional food in

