494 the evening (unless they are treating hypoglycemia). They will be asked to take a
495 picture of the dinner meal and identify their food and portion sizes. If they have a
496 smart phone (Android or Apple), they may download Calorie Mamma® or Calorie
497 King® to help them in calculating carbohydrates, protein and fat from the meal.
498 They will do this for each of their dinner meals on each of the days they are doing
499 the breakfast study, and for the breakfast meals they are eating each morning as
500 part of the pharmacodynamic testing. They will change their infusion set before
501 dinner prior to the first day of starting a standard breakfast, i.e., if they work from
502 Monday to Friday, this could be done on Sunday.

503

504 They are blinded to the insulin and the insulin dose decisions for these meals is also
505 not under their control since: 1) The overnight insulin delivery is not under their
506 control, 2) The timing of the meal bolus will be the same for all mornings, the dose
507 will be given immediately before eating, 3) Their dose of insulin will be determined
508 by their pump using their preset insulin-to-carbohydrate ratio and they will be eating
509 the same amount of carbohydrates each morning. They also will not be getting a

510 correction dose of insulin in the morning because they are using the closed-loop
511 controller overnight. If they required a correction dose of insulin, we will not use the
512 data from that morning in our data analysis. We will assess during each of these
513 four weeks the time in-range (70-180 mg/dl), mean glucose, CV, and time <70
514 mg/dl.

515

516 At the end of each two week period of blinded insulin use the participants and the
517 health care providers will be given a questionnaire asking them which insulin they
518 thought they were using, and if they had noticed any advantages to disadvantages
519 while they were using this insulin, and whether they would have wanted to make
520 any changes to their insulin delivery settings while using the insulin.

521

522

523 **Part 2: Extended Use Optimization Study**

524

525 To be eligible for Part 2 one of the inclusion criteria will be that the subject is
526 currently using Fiasp® insulin under their usual care. Subjects for Part 1 may
527 participate in part 2, and we will also recruit subjects outside of part 2 who are
528 currently using a 670G pump and taking Fiasp insulin. They will download their

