648 device event that is both serious and unexpected. Notification will be made within
649 10 days after becoming aware of the event.

650
651 [name] will inform the IRB of serious study-related adverse events and
652 abide by any other reporting requirements specific to their IRB.

653
654 **Potential Risks and Side Effects**

655 There may be a higher frequency of hypoglycemia immediately following a meal bolus.
656 There may be prolonged hyperglycemia following a high fat meal. There may be local tissue

657 reactions at the FIASP® infusion sites. Infusion sites may need to be changed more
658 frequently than usual when infusing FIASP®. As with any insulin, there is a risk for both
659 high and low blood glucose levels occurring if there is a mismatch between your insulin
660 needs and the insulin levels provided by the insulin. See hypoglycemia and hyperglycemia
661 risks below. It is very rare, but allergic reactions to insulin may occur.

662

663 **Risk of Hypoglycemia**

664 As with any person having insulin-dependent diabetes, there is always a risk of
665 having a low blood sugar (hypoglycemia). The frequency of nocturnal
666 hypoglycemia should be no more than it would be as part of daily living with
667 diabetes. Symptoms of hypoglycemia can include sweating, jitteriness, and not
668 feeling well. Just as at home, there is the possibility of loss of consciousness or
669 seizures (convulsions) and that for a few days you may not be as aware of
670 symptoms of low blood sugar. Even if severe low blood sugar does occur, it almost
671 always goes away quickly with treatment to raise the blood sugar.

672

673 **Risk of Hyperglycemia**

674 As with any person having insulin-dependent diabetes, there is always a risk of
675 having a high blood sugar (hyperglycemia). The frequency should be no more than
676 it would be as part of daily living with diabetes.

677

678 **Protection Against Risks and Treatment of Side Effects:**

679 Subjects will be given descriptions of possible side effects from wearing an infusion
680 set, and local side effects with insulin infusion sets or Guardian sensor insertion
681 sets. They will be told to contact the study staff if they see any signs of a skin
682 reaction. Based on the severity of local skin reaction, topical anti-inflammatory
683 medications can be used (such as topical steroids).

684

685 **Other Risks**

686 Some subjects may develop skin irritation or allergic reactions to the adhesives

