727 Withdrawal of a subject will be considered for the following reasons: 1) Failure to
728 monitor their sensor and infusion sites on a daily basis; 2) developing >1.0 mmol/L
729 ketones on 2 or more occasions and failing to change their infusion set or a single
730 episode of diabetic ketoacidosis due to an infusion site failure. For subjects who
731 withdraw or who are withdrawn, their data will be used for analysis purposes up until
732 the time of withdrawal.

733

734 **Confidentiality**

735 For security and confidentiality purposes, subjects will be assigned an identifier that
736 will be used instead of their name. De-identified subject information may also be
737 provided to Medtronic Diabetes.

738

739 **Level of Risk**

740 This research proposal in children is consistent with United States Department of
741 Health and Human Services, Protection of Human Subjects, Subpart D, Section
742 46.404 (Research not involving more than minimal risk).

743

744 **Planned Duration of the Entire Study**

745 Planned duration of the entire study will be 6 months.

747 **CHAPTER 6: STATISTICAL CONSIDERATIONS**

748

749 This is a pilot study to determine if there are any clinical issues with using Fiasp® in
750 the 670G hybrid closed-loop system. These studies are not statistically powered.

751

752 In the blinded cross-over studies (Part I) we will use data obtained during the
753 second week of each arm to compare the following measurements using a mixed-
754 effects model accounting for crossover study design of the study with the sequence
755 of treatment nested within the patient:

756

a) time in range (70-180 mg/dl)

757

b) percent time <70 mg/dl,

758

c) mean glucose,

759

d) glucose CV,

760

e) total daily insulin dose,

761

f) total daily basal insulin,

762

g) insulin delivery from MN to 6AM, and 6AM to MN

763

764 We will test to see if there is any difference in pharmacodynamics when using
765 Fiasp® in the home environment when they are eating their usual breakfast.

766

767 Insulin pharmacodynamics following the standard breakfast will be assessed by
768 measuring the peak glucose concentration (C_{max}), time to C_{max} (t_{max}), and estimated
769 average glucose excursions were assessed using sensor glucose values at a time
770 interval of 0 to 180 minutes after breakfast bolus. If a bolus was given between
771 120-180 minutes following the breakfast bolus, CGM values were only used up to

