772 the time of the bolus. The glucose at the time of the breakfast bolus (Time 0) will be
773 set to 0 mg/dL for each meal, and the remaining CGM values were adjusted
774 proportionally to allow analysis of postprandial glucodynamic parameters. We will
775 utilize a mixed-effects model accounting for crossover study design of the study with
776 the sequence of treatment nested within the patient. Breakfast meals are excluded
777 from postprandial analysis if: 1) the rate of change was greater than 0.3mg/dL/min
778 in the 1 hour prior to breakfast, 2) subjects gave a subsequent bolus prior to 120
779 minutes following the breakfast bolus, or 3) subjects deviated from their typical
780 breakfast. Dinner meals will be assessed when there has been no additional food
781 intake after dinner. The duration of insulin delivery to cover the meal will be
782 determined by the time it takes the post prandial glucose to reach 160 mg/dL
783 beyond 1 hour of eating. The peak glucose will also be recorded.

783

784 During the 6 week optimization study (Part II) we will use data obtained during the
785 first two weeks of the study (before data was reviewed and changes made by the
786 investigators) to data obtained during the last two weeks of the 3 month optimization
787 period. We will compare the following measurements using paired t-tests for data
788 with a normal distribution and a Mann-Whitney rank sum test for data that is not
789 normally distributed:

790

a) time in range (70-180 mg/dl)

791

b) percent time <70 mg/dl,

792

c) mean glucose,

- 793 d) glucose CV,
- 794 e) total daily insulin dose,
- 795 f) total daily basal insulin,
- 796 g) insulin delivery form MN to 6AM, and 6AM to MN
- 797 h) CHO:I ratios at breakfast, lunch and dinner
- 798 i) Active insulin time
- 799 j) Number of days between infusion set changes
- 800 k) Erythema (mm) and induration (mm) at infusion sites when they are changed
- 801 l) Average daily insulin, and mean glucose for each day of infusion set wear
- 802 m) Number of episodes of unexplained hyperglycemia in the first month vrs the
- 803 last month
- 804
- 805
- 806
- 807

808 **CHAPTER 7: REFERENCES**

809

- 810 1. Heise T, Hovellmann U, Nosek L, Sassenfeld B, Thomsen KMD, Haahr H.
811 Pharmacokinetic Properties of Fast-acting Insulin Aspart Administered in Different
812 Subcutaneous Injection Regions: Response to the commentary by Nuggehally R. Srinivas.
813 Clinical drug investigation 2017.

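### The Part 1 breakfast test drops the 3-hour no-eating instruction of the study it copies, so unbolused snacks and hypoglycaemia carbohydrate can enter the 0-180 minute window unrecorded

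*Combined protocol and SAP*

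**What the plan says.** Chapter 6 (Statistical Considerations) assesses the Part 1 standard breakfast by Cmax, tmax and average excursion, using sensor glucose over an "interval of 0 to 180 minutes after breakfast bolus. If a bolus was given between"; the sentence continues "120-180 minutes following the breakfast bolus, CGM values were only used up to" the time of that bolus. Whole breakfasts are excluded for a rate of change above 0.3 mg/dL/min "in the 1 hour prior to breakfast, 2) subjects gave a subsequent bolus prior to 120", and the list goes on "minutes following the breakfast bolus, or 3) subjects deviated from their typical" breakfast. Chapter 3 (Part 1) adds one more exclusion, explained by use of the closed-loop "controller overnight. If they required a correction dose of insulin, we will not use the" data from that morning.

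This is nearly the method text of section 1.2.3, which describes an earlier hyaluronidase study. In that study, "they were instructed not to eat for at least 3 hours following breakfast".

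In the Chapter 3 procedure for meal testing, subjects eat the same breakfast on three days per insulin. Nothing is said about food after it. On the same days they "will be asked to have a dinner with at least 30 grams of fat and no additional food in" the evening, with an exception for treating hypoglycaemia. Chapter 6 then assesses dinners only where nothing further was eaten. Pictures and portions are requested for the test breakfasts and dinners, and for no other food.

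Chapter 4 (Potential Risks and Side Effects) states: "There may be a higher frequency of hypoglycemia immediately following a meal bolus".

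**The concern.** A 0-180 minute glucose trace describes the insulin's effect on the breakfast only if the breakfast is the only carbohydrate in the window. The earlier study secured this by instruction. Part 1 keeps the window and the outcomes but not the instruction.

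Breakfast pharmacodynamics is named in the title of Part 1. Unrecorded later food would add noise under both insulins. If carbohydrate for lows is taken more often on one insulin, it would raise that insulin's average excursion, and sometimes its Cmax or tmax. An early low would then look partly like a weaker meal effect. Because the food is not logged, analysts could not correct for it afterwards.

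**Working it through.** The plan gives no power, effect size or rate for this comparison, so there is no figure to reproduce. The check is first of the text, then an illustration on assumed inputs.

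**1. The three meal tests side by side**

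| | Section 1.2.3 study, breakfast | Part 1 breakfast | Part 1 dinner |
|---|---|---|---|
| Instruction on later food | none for at least 3 hours | none given | none that evening, hypoglycaemia treatment excepted |
| Analysis rule triggered by later food | none stated | none stated | assessed only without further intake |
| Analysis rule triggered by a later bolus | dropped before 120 min, truncated at 120-180 min | same | none stated |

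**2. What happens to each event after a Part 1 test breakfast**

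- Snack with a bolus before 120 minutes: meal dropped.
- Snack with a bolus at 120-180 minutes: trace truncated.
- Correction dose required: that morning's data not used.
- Snack without a bolus: no clear rule and no requested record. Deviation from the typical breakfast reads most naturally as being about the breakfast itself.
- Carbohydrate for a low: no clear rule and no requested record.

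The gap is the last two events.

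**3. Illustrative size**

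Assumptions, none from the documents: extra carbohydrate adds X = 20-60 mg/dL; it is taken at t = 60-120 minutes; the rise is linear over 30 minutes and then held to 180 minutes; the share of affected breakfasts differs between insulins by d = 0.05-0.20. With up to 20 subjects and three breakfasts per insulin there are at most 20 × 3 = 60 breakfasts per insulin, so d corresponds to 3-12 breakfasts.

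Average excursion, one affected meal: X × [0.5 × 30 + (180 − t − 30)] / 180.

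- Smallest (X = 20, t = 120): 20 × (15 + 30) / 180 = 5.0 mg/dL.
- Largest (X = 60, t = 60): 60 × (15 + 90) / 180 = 35.0 mg/dL.

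Shift in the between-insulin mean = d × the per-meal shift: 0.05 × 5.0 = 0.25 to 0.20 × 35.0 = 7.0 mg/dL.

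Cmax, ceiling = d × X: 0.05 × 20 = 1 to 0.20 × 60 = 12 mg/dL. This is a ceiling because it adds the full rise to every affected peak.

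If the affected shares are equal (d = 0), this additive model gives no bias in the mean difference. Noise remains, and tmax can still move later.

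**4. When Cmax would move**

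Carbohydrate taken at a glucose below 70 mg/dL brings it to below 70 + 60 = 130 mg/dL at the top of the assumed range. Mean Cmax in Table 2 is 36.9 to 72.0 mg/dL above the pre-meal value. With an assumed pre-meal glucose of 100-140 mg/dL, the average meal peak is about 137-212 mg/dL. A low treated after the peak therefore usually leaves Cmax and tmax unchanged. They move mainly when the low comes before the meal peak.

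**5. Scale**

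The Cmax differences in Table 2 (standard minus hyaluronidase) are 69.5 − 43.5 = 26.0, 72.0 − 36.9 = 35.1 and 51.6 − 56.4 = −4.8 mg/dL, with p = 0.296, 0.167 and 0.681. They come from another intervention and serve only as a yardstick.

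**The case against.** The strongest reply is that the gap is narrow and its effect unproven. The 670G expects meals to be announced and bolused, so many snacks would be caught by the bolus rules. The study is an unpowered pilot of a usual breakfast at home. The closed loop also adjusts basal insulin, which the simple arithmetic ignores. All of this stands, and it limits the weight of the point. It does not supply a rule or a record for unbolused food, and the protocol itself thought both an instruction and an analysis condition necessary for dinner.

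Three stronger readings are tempting, and the documents do not support them.

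- A reader might infer that the protocol predicts more lows on Fiasp, and so a known bias against it. Chapter 4 says only that such lows may be more frequent. It gives no rate and no expected difference between insulins.
- A reader might infer that the pilot would miss hypoglycaemia or report its opposite. Percent time below 70 mg/dL is a listed outcome for the second week of each arm, the week of the meal tests. Average excursion also falls when glucose falls; Table 2 shows values of −6.7 and −5.4. What is missing is a measure of lows specific to the breakfast window.
- A reader might take the Cmax figures as estimates of bias. They are ceilings on assumed inputs.

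One could also object that truncating every trace at the first carbohydrate would do harm. That is right for treated lows: an early low would cut the trace before the meal peak, lowering Cmax and shortening tmax for the very insulin that caused the low.

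**Conclusion.** The gap is real. Part 1 takes over the 0-180 minute breakfast method without the no-eating condition that made it interpretable, and gives breakfast neither of the two protections it gives dinner. Only unbolused snacks and hypoglycaemia carbohydrate are affected.

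The consequence is noise in both arms, plus a possible bias in average excursion, and sometimes in Cmax or tmax, if treated lows differ between insulins. Neither the direction nor the size can be established from the documents. The ranges in the working rest wholly on the assumed rise, timing and difference in shares. The omission itself is certain; the bias is only possible. In an unpowered pilot this is a change worth making, because it alters what subjects do and record and cannot be repaired after data collection. It does not undermine the design.

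**What to change.** **Chapter 3, procedure for meal testing.** Carry over the instruction from section 1.2.3: no food for 3 hours after each test breakfast, with the hypoglycaemia exception already used for dinner, so that treatment of lows is unaffected. Ask subjects to log the time and grams of any carbohydrate taken in that window, and whether it was for a low.

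**Chapter 6, breakfast analysis.**

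- Exclude or truncate breakfasts with a logged snack that was not hypoglycaemia treatment, stating which, in parallel with the existing dinner and bolus rules.
- Keep breakfasts with hypoglycaemia treatment in the main analysis, flag them, and report their number by insulin. Show truncation at the treatment time only as a sensitivity analysis. Keeping these meals does not remove the effect of the carbohydrate; it makes that effect visible.
- Add the 0-180 minute glucose nadir and percent time <70 mg/dL for all test breakfasts.

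**Cost.** One sentence in the instructions, one line on the meal log, and two summaries from CGM data already collected. Subjects carry a slight extra burden on 3 × 2 = 6 mornings, and a few windows will be lost or shortened.

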200 *AUC=Area under the Curve (mg/dL)

201 °Cmax=Peak glucose concentration (mg/dL)
202 ‡Tmax=Time to peak glucose concentration (minutes)
203 *represents statistical significance (i.e. P<0.05)
204

205 **Figure 1-5:** Postprandial glucose profiles by Day of infusion set wear (and hours
206 following hyaluronidase infusion)

207
208
209

210 **1.3 Study Overview**

211

212 *Use of Fiasp®:* Fiasp® insulin has been approved for sale in the USA, and has been
213 available since February 7th 2018. Although it is not approved for pumps, it will be used in
214 pumps off-label because of it has a more rapid onset of action. The 670G closed-loop
215 system automatically adjusts basal rates throughout the day and night to minimize hyper
216 and hypoglycemia. Use of the 670G provides a unique opportunity to assess how Fiasp®
217 works in a closed-loop system and to determine if any changes need to be made to the
218 670G pump to optimize the use of Fiasp®.

219

220 According to the FDA guidelines we do not think this study requires an IND since we meet
221 all of the following six conditions:

- 222 i. it is not intended to be reported to FDA in support of a new indication for use or to
223 support any other significant change in the labeling for the drug;
- 224 ii. it is not intended to support a significant change in the advertising for the product;
- 225 iii. it does not involve a route of administration (it is still being given subcutaneously) or
226 dosage level, use in a subject population, or other factor that significantly increases
227 the risks (or decreases the acceptability of the risks) associated with the use of the
228 drug product;
- 229 iv. it is conducted in compliance with the requirements for IRB review and informed
230 consent [21 CFR parts 56 and 50, respectively];
- 231 v. it is conducted in compliance with the requirements concerning the promotion and
232 sale of drugs [21 CFR 312.7]; and
- 233 vi. it does not intend to invoke 21 CFR 50.24.”

234

235

236 **1.4 Protocol Synopsis:**

237

238 This is a pilot outpatient study conducted at Stanford to obtain preliminary data on
239 how Fiasp® works in a closed-loop system. The plan will be to enroll up to 20
240 subjects for each part of the study. Part 1 is a blinded cross-over study to assess
241 how well Fiasp® insulin works when used with the 670G pump compared to aspart
242 insulin and will take 6 weeks for a subject to complete. Part 2 is a Fiasp®

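### Breakfast outcomes: state that Time 0 glucose is subtracted, and estimate its slope for Cmax and average excursion rather than fixing it at 1

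*Combined protocol and SAP*

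**What the plan says.** Chapter 6 (Statistical Considerations) names three outcomes for the Part 1 standard breakfast: Cmax, tmax and estimated average excursion, from sensor glucose over 0 to 180 minutes after the bolus. Glucose at the bolus (Time 0) is "set to 0 mg/dL for each meal, and the remaining CGM values were adjusted" "proportionally to allow analysis of postprandial glucodynamic parameters. We will". No formula follows.

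The analysis will "utilize a mixed-effects model accounting for crossover study design of the study with" "the sequence of treatment nested within the patient. Breakfast meals are excluded". No Time 0 term is named, and the fixed effects are not listed.

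A breakfast is dropped "from postprandial analysis if: 1) the rate of change was greater than 0.3mg/dL/min" over the preceding hour. Chapter 3 also drops mornings that needed a correction dose. The first rule limits drift before the meal, not the starting level. The second removes some mornings but does not equalise the starts of those that remain.

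Section 1.4 gives the size of the study, whose purpose is to learn "how Fiasp® works in a closed-loop system. The plan will be to enroll up to 20" subjects for each part. Under the Chapter 3 meal-testing procedure, subjects "have 3 days with a consistent breakfast that is the same for all 6 days they are" tested, three on each insulin, during the second week on each blinded insulin.

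**The concern.** There are two linked problems.

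- **Wording.** Multiplying a positive glucose value by a constant gives 0 only if the constant is 0, and that erases the whole curve. An analyst must therefore replace the written rule with another one.
- **Fixed slope.** If the replacement is subtraction, starting glucose enters Cmax and average excursion with a coefficient of exactly 1, because nothing in the described model estimates it. If later glucose rises by less than 1 mg/dL per 1 mg/dL of starting glucose, a higher start gives a smaller subtracted rise whichever insulin is in use. Chance differences in starting glucose then add noise, and a systematic difference between insulins moves the estimated contrast.

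With at most 20 subjects and three breakfasts per insulin before exclusions, avoidable noise is worth removing. If the model is not fixed in advance, the choice between adjusted and unadjusted results could be made after they are seen.

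**Working it through.** The plan gives no power, interval width, SD or correlation for these outcomes, so there is no stated figure to reproduce.

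**1. Which adjustment is meant.** Let G0 be Time 0 glucose and G(t) a later value. Scaling needs k × G0 = 0 with G0 > 0, so k = 0. Two workable rules remain: G(t) − G0 in mg/dL, or (G(t) − G0)/G0 in percent. They differ. A 60 mg/dL rise from 100, 130 or 160 mg/dL is 60 each time by subtraction, but 60%, 46% or 38% as relative change.

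Section 1.2.3 describes the earlier hyaluronidase study with the same rule. Its Table 2 reports Cmax in mg/dL with means from 36.9 to 72.0, and average excursions that include −6.7 and −5.4. These cannot be absolute glucose values, and the unit is not percent. Subtraction fits. tmax is the same under both rules, because subtracting or dividing by a constant does not move the time of the peak.

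**2. Precision under subtraction.** Let sY be the SD of the later value, sB the SD of Time 0, k = sB/sY, and r their within-patient correlation.

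- Change score variance: sY² + sB² − 2·r·sY·sB
- Variance with Time 0 as covariate: sY²(1 − r²)
- Ratio, adjusted to change score: (1 − r²)/(1 + k² − 2rk)
- True slope: r/k

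With k = 1 the ratio is (1 + r)/2. With k = 0.5 it is (1 − r²)/(1.25 − r).

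| k (assumed) | r (assumed) | slope | variance ratio | variance saved | interval width × |
|---|---|---|---|---|---|
| 1 | 0.3 | 0.3 | 0.65 | 35% | 0.81 |
| 1 | 0.5 | 0.5 | 0.75 | 25% | 0.87 |
| 1 | 0.7 | 0.7 | 0.85 | 15% | 0.92 |
| 0.5 | 0.3 | 0.6 | 0.91/0.95 = 0.958 | 4% | 0.98 |
| 0.5 | 0.5 | 1.0 | 0.75/0.75 = 1 | 0% | 1.00 |
| 0.5 | 0.7 | 1.4 | 0.51/0.55 = 0.927 | 7% | 0.96 |

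The saving is zero when the slope is 1 and grows as the slope moves away from 1 in either direction.

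A simulated two-period crossover agrees with the k = 1 rows. It had 20 patients, three breakfasts per insulin, terms for patient, period and treatment, and 600 runs per setting. Interval widths were multiplied by 0.81, 0.87 and 0.93. At r = 0.98 the multiplier was 1.00, so the lost degree of freedom costs almost nothing.

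**3. In mg/dL.** Assume an SD of 35 for the rise (Table 2 Cmax SDs run from 25.9 to 48.8), a within-patient ICC of 0.3, 20 patients and three usable breakfasts per insulin. The variance of a patient's difference is 2 × 35² × 0.7/3 = 571.7. The 95% half-width is 2.101 × √(571.7/20) = 11.2 mg/dL. With r = 0.5 it becomes 11.2 × 0.866 = 9.7 if k = 1, and stays at 11.2 if k = 0.5.

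**4. Effect on the estimate.** If Time 0 differs by d between insulins, the change-score contrast equals the effect at a given start plus (slope − 1) × d. With slope 0.5, d = 8 mg/dL and an effect of −10 (all assumed), this is −10 + (−0.5)(8) = −14. The simulation gave −14.1 unadjusted and −10.0 adjusted.

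**The case against.** **The meaning can be recovered.** This stands. The unit and Table 2 point to subtraction. A reader might infer that the breakfast outcomes are ill-defined, or that a percent scale is planned. The documents do not support that: the text puts Time 0 at 0 mg/dL, and the earlier results are in mg/dL. tmax is not affected at all.

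**Time 0 is not ignored.** This also stands. Subtraction uses Time 0; what is missing is an estimated slope. Chapter 6 names only the crossover structure, so the absence of a Time 0 term is read from its silence.

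**The precision loss is not established.** A reader might infer that the intervals will be wider by a known and sizeable amount. The documents give neither the correlation nor the SD ratio. Equal SDs are open to doubt, because Time 0 follows overnight closed-loop control and both drifting and correction-dose mornings are removed. With a Time 0 SD half the peak SD, the gain is small or nil. No source in the documents shows that the slope is below 1.

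**The covariate is not neutral.** This is the strongest objection. Time 0 is recorded in the second week on each blinded insulin, after a night of closed-loop delivery of that insulin, and Part 1 exists to see how the system adapts. Treatment may therefore shift Time 0, and adjusting for it changes the quantity estimated as well as the interval. So the change is not free. It does not favour leaving the text alone, though: subtraction also corrects for Time 0, with an untested slope of 1.

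**It is an unpowered pilot.** True, and it limits how serious the point is. Chapter 6 still plans to test for a difference, and the product of a pilot is its estimates and their precision.

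**Conclusion.** The point holds in two parts of unequal weight. The wording cannot be carried out literally, but its intended meaning is clear enough that this is a clarification. The more substantive part is that the described breakfast model fixes the slope on starting glucose at 1 for Cmax and average excursion. Estimating the slope costs one degree of freedom, does not otherwise lose precision when starts differ by chance, and removes the linear dependence on starting level when the true slope is not 1.

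The size is unknown from the documents. Over the assumptions tabulated, the variance saved runs from 0% to 35%. The precision argument does not extend to tmax. This is a cheap improvement with a caveat on interpretation; it does not show that the planned comparison is invalid.

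**What to change.** - In Chapter 6, replace the proportional adjustment with: 'Time 0 value subtracted from each later value (mg/dL)'.
- Write out the breakfast model for Cmax and average excursion: treatment, period, sequence, random patient, and Time 0 glucose as a covariate, ideally split into patient mean and within-patient deviation. The argument here gives no reason to add Time 0 to the tmax model.
- Report Time 0 glucose by insulin.
- Give the unadjusted change as a sensitivity analysis.
- Describe the adjusted result as the meal effect at a given starting glucose, and note that starting glucose may itself respond to the insulin.

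The cost is a few lines of text, one degree of freedom (or two if the covariate is split) and one further analysis. Time 0 is already recorded by the sensor, so no visit or measurement is added.
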